4.2 Exclusion Criteria

Subjects who meet any of the following criteria at Screening will be excluded from the study:

1. At Screening or Baseline (Day 0), plasma ammonia level ≥ 100 $\mu\text{mol/L}$ for patients who historically maintain normal ammonia levels; OR plasma ammonia level ≥ 200 $\mu\text{mol/L}$ for patients who historically are not able to fully control ammonia levels with baseline management; OR signs and symptoms of hyperammonemia, with documented elevated ammonia level, during the 4-week period preceding Day 0. If the ammonia level is inconsistent with the subject's clinical status, the ammonia level may be repeated to ensure accurate results.
2. Liver transplant, including hepatocyte cell therapy/transplant.

Protocol: 301OTC01

3. History of liver disease as evidenced by any of the following: portal hypertension, ascites, splenomegaly, esophageal varices, hepatic encephalopathy, or a liver biopsy with evidence of stage 3 fibrosis.
4. Significant hepatic inflammation or cirrhosis as evidenced by imaging or any of the following laboratory abnormalities: alanine aminotransferase (ALT) or aspartate aminotransferase > the upper limit of normal (ULN), total bilirubin > $1.5 \times$ ULN, alkaline phosphatase > $2.5 \times$ ULN.
5. Serum creatinine > 2.0 mg/dL.
6. Evidence of active hepatitis B virus (HBV) or hepatitis C virus (HCV) infection, documented by current use of antiviral therapy for HBV or HCV or by hepatitis B surface antigen (HBsAg) or HCV RNA positivity. **NOTE:** Subjects with a history of HCV infection must have documentation of 2 negative viral assays by polymerase chain reaction (PCR), collected at least 6 months apart, to be considered negative for HCV. Subjects with a history of HCV infection who test positive for HCV RNA at Screening can be rescreened once, after they have been treated and have documentation of at least 2 negative samples collected at least 6 months apart.
7. History of human immunodeficiency virus (HIV) infection AND any of the following: CD4+ cell count < 350 cells/mm³, change in antiretroviral therapy regimen within 6 months prior to Day 0, or plasma viral load > 200 copies/mL, documented on 2 separate occasions, as measured by PCR.
8. Active infection (viral or bacterial).
9. Anti-AAV8 neutralizing antibody titer \geq 1:5.
10. Participation (current or previous) in another gene transfer study.
11. Participation in another investigational medicine study within 3 months of Screening.
12. History of a malignancy for which the subject has received treatment in the past 2 years except for prostate cancer treated with watchful waiting or surgically removed non-melanoma skin cancer.
13. Has a positive serum pregnancy test at Screening (females of childbearing potential only), a positive urine pregnancy test at Baseline (Day 0; females of childbearing potential only), or is nursing.
14. Has any other significant medical condition that the investigator feels would be a risk to the subject or would impede the study.

5 Screening and Randomization Procedures

5.1 Subject Screening

All potential subjects will sign an informed consent form (ICF) before any study procedures or assessments are performed or initiated (Section 11.3). Subjects will have the opportunity to have any questions answered before signing the ICF. All questions raised by the subject must be addressed before the investigator also signs the ICF. A copy of the signed ICF will be given to the subject.

Subjects will be administered [1-¹³C]sodium acetate orally. Blood samples for determination of ureagenesis will be collected, via an indwelling catheter, before dosing (time 0) and at approximately 0.5, 1, 1.5, 2, 3, and 4 hours after dosing with [1-¹³C]sodium acetate. During Screening, assessment of rate of ureagenesis may be repeated if discrepant with a subject's clinical status and severity.

Prior to the start of DTX301 infusion, the study site must confirm that the subject's plasma ammonia level on Day 1 (predose) is < 100 µmol/L for patients who historically maintain normal ammonia levels, and the subject is clinically stable; OR the subject's plasma ammonia level on Day 1 (predose) is < 200 µmol/L, for patients who historically are not able to fully control ammonia levels with baseline management, and the subject is clinically stable. If the subject is deemed clinically unstable, dosing with DTX301 will be held, and the subject can be rescreened once the subject is determined to be clinically stable, with repeat of relevant assessments or rescreened at a later date (Section 3.2.1).

Subjects with a history of HCV infection who test positive for HCV RNA at Screening can be rescreened once, after they have been treated and have documentation of at least 2 negative samples collected at least 6 months apart. **NOTE:** To be eligible to participate in the study, subjects must have 2 negative HCV viral assays by PCR at least 6 months apart.

Study sites will maintain documentation of all potential subjects screened for inclusion in the study. If a subject is excluded from the study, the reasons for exclusion will be documented in the subject's source documents and on the screening log.

5.2 Subject Randomization

This is an open-label study; 3 subjects will be enrolled into Cohort 1 and then, sequentially, into cohorts of a minimum of 2 to 3 subjects each, up to Cohort 3. Dosing of additional subjects in expansion of Cohort 3, and initiation of Cohort 4 (Dosing Process Optimization) may occur in parallel (Section 3.1) with at least 1 male subject assigned to each.

6 Study Treatment

6.1 Identity of DTX301

6.1.1 Description of DTX301

DTX301 is a nonreplicating, self-complementary, recombinant AAV8 vector that contains a codon-optimized, wild-type human OTC coding sequence. DTX301 demonstrates thermal stability, which is a general property of AAV and parvoviruses. DTX301 is supplied as a slightly [REDACTED] [REDACTED] DTX301 is a homogeneous, monodisperse solution that is clear and colorless without visible particulates.

6.1.2 Components Used for Manufacturing DTX301

[REDACTED]
[REDACTED]

- [REDACTED]
- [REDACTED]
[REDACTED]
- [REDACTED]

[REDACTED]. For additional information, please refer to the DTX301 investigator's brochure.

6.2 Management of Clinical Supplies

The study site will be provided supplies required for the infusion of DTX301.

6.2.1 Packaging and Labeling

Each vial of study product provided to study sites will contain 1 mL of DTX301 frozen in 2 mL sterile glass vials with a primary label on the vial. Study product will have secondary packaging with a secondary label. The primary label meets all requirements for blister and small packaging units and will contain a unique identifier. The secondary label will contain required text for all countries participating in the study and will also contain a unique identifier. Secondary labeling will appear in the appropriate language for the country supplied.

6.2.2 Storage of Study Product

6.2.2.1 Storage of DTX301

DTX301 must be stored in a secure freezer at a controlled temperature at or below [REDACTED] C. The study site is to maintain a daily log documenting the temperature.

6.2.3 Study Product Accountability

The investigator or designated personnel will maintain accurate records of receipt of all study product (DTX301), including dates of receipt. In addition, accurate records will be kept regarding when and how much study product is dispensed and used by each subject in the study. Reasons for departure from the expected dispensing regimen must also be recorded. At the completion of the study, all study product will be reconciled and retained or destroyed according to instructions provided by the sponsor.

6.2.4 Transmission of Infectious Agents

Recombinant AAV vectors are nonreplicative and are not expected to pose a risk of transmission. However, all sexually active subjects must use approved contraception from the time of DTX301 dosing and for 52 weeks following administration (Section 4.1). All subjects enrolled in the study should be encouraged to discuss the use of approved contraception with his or her partner in order to prevent possible transmission of vector via seminal or vaginal fluid. The study product and posttreatment study samples should be handled using standard universal precautions.

6.2.5 Exposure to Radiation

Carbon-13 is a naturally occurring, stable isotope of carbon that emits no radioactivity, has no known adverse biological effects, and is safe to use in children and adults [Koletzko 1997; Tuchman 2008b].

Detailed instructions for dose preparation and administration of [1-¹³C]sodium acetate are provided in the ureagenesis manual.

6.3 Treatment Schedule and Administration

6.3.1 Administration of [1-¹³C]Sodium Acetate

Subjects will be administered [REDACTED] [1-¹³C]sodium acetate dissolved in 60 mL of water at the time points specified in the Schedule of Events (Table 15-1).

The dose of [1-¹³C]sodium acetate administered will be calculated using the subject's weight recorded at Screening. Prior to oral administration, calculations will be checked by the study site pharmacist and a member of medical personnel charged with administration of [1-¹³C]sodium acetate.

The subject's plasma ammonia level should be < 100 µmol/L or within the range of historical ammonia levels obtained when the subject was clinically stable in order to receive [1-¹³C]sodium acetate (Section 8.2.4.1; Section 4.1). If the ammonia level is inconsistent with the subject's clinical status, the ammonia level may be repeated to ensure accurate results. If the subject is deemed clinically unstable, administration of [1-¹³C]sodium acetate will be held until the subject is determined to be clinically stable.

Subjects may experience a temporary, mildly unpleasant salty and/or acidic taste from the sodium acetate component of the compound. The study site must be equipped with emergency resuscitation capabilities. Any event that is considered an AE associated with the administration of [1-¹³C]sodium acetate (Section 9.1.1) should be recorded in the appropriate page of the eCRF (Section 9.1.2).

Sodium acetate is the sodium salt of acetic acid, a naturally occurring metabolite. Sodium acetate is a commonly used food additive (E 262).

Detailed instructions for dose preparation and administration of [1-¹³C]sodium acetate are provided in the ureagenesis manual.

6.3.2 Administration of DTX301

Subjects will receive a single, peripheral IV infusion of DTX301, administered by qualified study personnel as designated by the investigator (Table 15-1). The dose will be determined by the cohort and candidate dose (Section 3.1).

The dose of DTX301 to be administered will be calculated using the subject's weight recorded at Screening. The subject's weight will be verified prior to administration of DTX301 to ensure that their current weight is within 10% of their screening weight. **NOTE:** Any subject weighing > 100 kg (> 220 lb) will be dosed as if his or her weight is 100 kg. Prior to infusion, all infusion bag labels will

Protocol: 301OTC01

be checked by the study site pharmacist and a minimum of 2 medical personnel charged with administration of DTX301. **NOTE:** Study product should not be prepared for infusion until the subject's plasma ammonia level on Day 1 is confirmed to be less than 100 µmol/L or within the range of historical ammonia levels obtained when the subject was clinically stable (Section 4.1).

The study site must be equipped with emergency resuscitation capabilities. On Day 1, an IV catheter will be inserted into a peripheral vein and flushed with saline.

Detailed instructions for dose preparation and subsequent infusion of DTX301 are provided in the pharmacy manual.

6.3.3 Treatment Compliance

[1-¹³C]sodium acetate will be administered orally at the study site and observed by qualified personnel. The dose and time of administration will be recorded in the subject's eCRF. Adherence to baseline ammonia scavenger medication regimens and modifications to ammonia scavenger medication regimens (Section 3.2.4) and protein-restricted diet (Section 3.2.5) is also considered treatment compliance.

DTX301 will be administered at the infusion center via a single IV infusion administered by qualified personnel. The dose, start time, stop time, and volume of infusion will be recorded in the subject's eCRF.

6.4 Prior and Concomitant Therapy

Use of all prior and concomitant medications will be recorded in the subject's eCRF. The minimum requirement is that the drug name, the dates of administration, and the reason for use are to be recorded. This will include all prescription drugs, herbal products, vitamins, minerals, and over-the-counter medications. Any changes in concomitant medication use will also be recorded in the subject's eCRF.

6.4.1 Permitted Medications

The use of permitted medications (date, dosage, reason for therapy) will be recorded on the concomitant medication page in the eCRF.

If a subject starts a new medication, including medications to alleviate complications associated with OTC deficiency and herbal supplements, it should be discussed with the investigator.

Protocol: 301OTC01

Any concomitant medication deemed necessary for the welfare of the subject during the study may be given. It is the responsibility of the investigator to ensure that details regarding the medication are recorded in full in the eCRF.

6.4.2 Prohibited Medications

Use of any of the following medications is prohibited, unless the investigator feels these medications are medically indicated. If medically indicated, the use of prohibited medications (date, dosage, reason for therapy) will be recorded on the concomitant medication page in the eCRF:

- Another investigational product to treat OTC deficiency;
- Another gene therapy product; or
- Any other medication currently under investigation.

7 Withdrawal of Subjects From the Study

7.1 Study Withdrawal

Subjects may withdraw from the study at any time and for any reason without prejudice to their future medical care by the investigator or at the study site. Any subject who withdraws consent to participate in the study will be removed from further treatment and/or study observation immediately upon the date of request.

The investigator must record the reason for withdrawal on the relevant page in the eCRF. The reason for withdrawal may include the following:

1. Withdrawal of consent
2. Administrative decision by the investigator or the sponsor
3. Ineligibility
4. Significant protocol deviation
5. Subject noncompliance
6. Adverse event

If a subject is withdrawn due to an AE, the investigator will arrange for the subject to have follow-up visits until the AE has resolved or stabilized (Section [9.1.5](#)).

If a subject requests or decides to withdraw from the study, all efforts will be made to complete and report the observations as thoroughly as possible up to the date of withdrawal, and an early withdrawal visit will be performed.

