3.2.8 End of Study

Subjects who complete all visits up to and including the Week 52 visit will have completed the study. Subjects who discontinue early will be asked to return for an early withdrawal visit, where all safety assessments should be performed (Table 15-1). Subjects with any ongoing AEs at this visit will continue to be monitored as outlined in Section 9.1.5. After completion of this study, subjects will be asked to enroll in a 4-year extension study to evaluate the long-term (a total of 5 years after dosing) safety and efficacy of DTX301.

4 Subject Selection

Subjects will be assigned to study treatment only if they meet all of the inclusion criteria and none of the exclusion criteria.

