13.2.2 Protocol Deviations

A deviation from the protocol is a departure from the written procedures or processes. **A significant deviation occurs when there is nonadherence to the protocol by the subject or investigator that results in a significant, additional risk to the subject or important change to the study design.** Significant deviations can include nonadherence to inclusion or exclusion criteria, nonadherence to safety and efficacy-related assessments, or nonadherence to FDA regulations or ICH GCP guidelines, that could lead to the subject being withdrawn from the study (Section 7.1). Protocol waivers or exemptions are not permitted. Adherence to the study design requirements, including those specified in the Schedules of Events (Table 15-1 and Table 15-2), is essential for study conduct.

Protocol: 301OTC01

The investigator or designee must document and explain in the subject's source documentation any deviation from the approved protocol. The investigator may implement a deviation from, or a change of, the protocol to eliminate an immediate hazard to study subjects without prior IRB/IEC/IBC approval. As soon as possible after such an occurrence, the implemented deviation or change, the reasons for it, and any proposed protocol amendments should be submitted to the IRB/IEC/IBC for review and approval, to the sponsor for agreement, and to the regulatory authorities, if required.

Protocol deviations will be documented by the clinical monitor throughout the course of monitoring visits. Principal investigators will be notified in writing by the monitor of deviations. The IRB/IEC/IBC should be notified of all protocol deviations in a timely manner, as required.

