3.2.9. Cohort size

The cohort size will be three evaluable patients in every case for cohorts 1 to 3 as the expansion of cohort 3 and cohort 4 is not part of the N-CRM assessment. A patient is classed as evaluable if the patient remained in the study for at least 12 weeks after dosing or a DLT was observed within 12 weeks of dosing. Should a protocol amendment change the inclusion / exclusion criteria of the study for safety, then a decision will be taken and documented on which patients to include in the CRM model to recommend the next dose after the study resumes. The N-CRM model will not be modified to take into account any protocol amendment that may be developed after the first N-CRM model has been run.

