8.1. Rate of Ureagenesis

This efficacy endpoint is defined as the change from baseline in rate of ureagenesis measured by the generation of ¹³C-urea over 4 hours as determined by isotope ratio mass spectrometry at Weeks 6, 12, 20, 24, Early Withdrawal, and End of Study (Week 52). The observed, change from baseline, and percent change from baseline in rate of ureagenesis will be summarized by DTX301 dose/prophylactic corticosteroids and visit based on the SS.

Rate of ureagenesis ($\mu\text{mol}\cdot\text{h}/\text{kg}$) for a given patient at a specific visit will be estimated using the following steps:

[REDACTED]

The association between change from baseline in rate of ureagenesis and DTX301 dose (2.0×10^{12} GC/kg, 6.0×10^{12} GC/kg and 1.0×10^{13} GC/kg) will be evaluated [REDACTED]

[REDACTED]

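### Protocol 7.1 and 13.2.2 let dosed subjects be removed for reasons other than consent, which ends collection of new adverse events before Week 52 while they stay in the AE denominator

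*Protocol*

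**What the plan says.** The primary objective is the safety of a single infusion, and subjects are to be followed for 52 weeks (Protocol 2 and 3.1).

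Protocol 7.1 states "The reason for withdrawal may include the following" and lists withdrawal of consent, administrative decision by investigator or sponsor, ineligibility, significant deviation, noncompliance and AE. Protocol 13.2.2 adds that significant deviations, including failures of eligibility, are ones "that could lead to the subject being withdrawn from the study". Under Protocol 6.3.3, adherence to scavenger and diet regimens, and to their permitted modifications, "is also considered treatment compliance". Protocol 7.2 expects some withdrawals after dosing and does not replace those subjects.

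Three provisions cover what happens next:
- For a withdrawal due to an AE, "the investigator will arrange for the subject to have follow-up visits until the AE has resolved or stabilized" (Protocol 7.1).
- "Subjects who discontinue early will be asked to return for an early withdrawal visit, where all safety assessments should be performed" (Protocol 3.2.8). Any AE ongoing at that visit is followed under Protocol 9.1.5.
- AEs are assessed only up to the end-of-study or early withdrawal visit (Protocol 9.1).

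On analysis, the Safety Set is all dosed subjects (SAP 4.15.1; also Protocol 10.5.3), and AE percentages use the number of subjects in the analysis set (SAP 9.1). For the dose-finding model (the N-CRM), "A patient is classed as evaluable if the patient remained in the study for at least 12 weeks after dosing", or if a dose-limiting toxicity (DLT) was seen within that time (SAP 3.2.9).

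**The concern.** In a repeated-dose trial, withdrawal for an AE or noncompliance at least stops further exposure. Here exposure is complete on Day 1, so removal from the study has only one effect: the subject is no longer observed. No text keeps a dosed subject under general safety observation to Week 52 after removal for one of these reasons. The extension study is offered after completion of this one, so the documents give a removed subject no stated route into long-term follow-up either.

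At stake is the primary endpoint. An event that starts after the early withdrawal visit is not collected, but the subject still counts in the denominator as someone without it. Some of the listed reasons can be related to outcome: an AE is directly so, and noncompliance or a deviation may be. With cohorts of 2 to 3, one truncated subject is a large share of the data.

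**Working it through.** The plan gives no figure to reproduce: the sample size is stated not to rest on a power calculation (SAP 4.9), and no withdrawal rate is assumed. The figures below show direction and size only.

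**1. Chain of provisions.** Removal after dosing is possible (Protocol 7.1, 7.2, 13.2.2). One early withdrawal visit follows. New AEs are then no longer collected (Protocol 9.1); ongoing AEs are followed (Protocol 3.2.8, 9.1.5). The subject remains in the denominator (SAP 4.15.1, 9.1), and the SAP states no exposure-adjusted AE rate.

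**2. Effect on crude incidence.** Take one type of AE with 52-week probability p = 0.25. That number is borrowed from the SAP 3.2.4 target toxicity rate purely as an example; there it applies to DLTs within 12 weeks. Assume a constant hazard and one subject removed at week w, with removal unrelated to that event.

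- Probability of observing the event in the removed subject: q(w) = 1 − (1 − p)^(w/52)
- Expected cohort incidence: [(n − 1)p + q(w)] / n
- q(12) = 1 − 0.75^(12/52) = 0.064; q(24) = 1 − 0.75^(24/52) = 0.124

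| Cohort size | Full follow-up | Removal at Week 12 | Removal at Week 24 |
|---|---|---|---|
| 3 | 25.0% | (0.50 + 0.064)/3 = 18.8% | (0.50 + 0.124)/3 = 20.8% |
| 2 | 25.0% | (0.25 + 0.064)/2 = 15.7% | (0.25 + 0.124)/2 = 18.7% |

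In relative terms the understatement at Week 12 is 25% (n = 3) or 37% (n = 2), and at Week 24 it is 17% or 25%.

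**3. Sensitivity to timing (n = 3, removal at Week 12).** If every such event starts before Week 12, q = 0.25 and nothing is lost: 25.0%. If every one starts after Week 12, q = 0 and expected incidence is 0.50/3 = 16.7%. The constant-hazard 18.8% lies between. Protocol 1.3.1 reports liver enzyme rises starting about 8 days to 7 weeks after dosing, so for that event a Week 12 removal costs essentially nothing.

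**4. Effect on the N-CRM.** Under SAP 3.2.9 a subject who leaves before Week 12 without a DLT is non-evaluable; one with a DLT in that window stays evaluable. I used the SAP 3.2.7 logistic model with its printed prior and reference dose 6 × 10^12 GC/kg, and assumed 0/3 DLTs at each of the two lower doses. The posterior mean p(DLT) at 1 × 10^13 GC/kg is:

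- 0/3 evaluable with DLT: 0.067; one DLT-free subject lost, 0/2: 0.074
- 1/3: 0.153; if the DLT would have occurred after that subject left, the model sees 0/2: 0.074

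Losing a subject who would have stayed DLT-free raises the estimate slightly. Losing one whose DLT was still to come halves it. All these values are below 0.25, so the highest candidate dose remains nearest to target in each.

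The evaluability rule is itself unsettled: SAP 4.15.1 names the whole Safety Set for N-CRM modelling, while SAP 3.2.9 restricts it to evaluable patients.

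**The case against.** The strongest reply is that Protocol 7.1 is mainly a list for recording reasons. It orders no removal, it also serves subjects who leave before dosing (where ineligibility naturally belongs), and an AE may be the subject's own reason for leaving. Protocol 13.2.2 speaks only of what could happen. An early withdrawal visit with full safety assessments is planned, and AEs ongoing then are followed. SAP 5.4 summarises duration of participation by cohort, and SAP 5.2 tabulates the reason for discontinuation. A subject removed for an AE already counts in the any-AE percentage, so the loss concerns other events. All of this stands and limits the size of the problem. It does not supply the missing statement that dosed subjects stay under observation.

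A reader might infer more than the documents support:

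- *That the safety endpoint loses subjects.* It does not; every dosed subject stays in the Safety Set.
- *That a subject whose scavengers or diet change with improvement or worsening can be removed for noncompliance.* Protocol 6.3.3 counts adherence to modifications under 3.2.4 and 3.2.5 as compliance, and those sections allow both reduction and reinstatement. Only adjustment without the site's guidance could be noncompliance.
- *That a lost subject pushes the model across the 0.25 target.* With one DLT at the second dose, losing a DLT-free subject there moves the posterior mean at 1 × 10^13 GC/kg from 0.222 to 0.253. But SAP 3.2.3 picks the dose nearest to 0.25 on either side, and that dose is the same in both cases (0.101/0.176/0.222 against 0.119/0.203/0.253). A change appears in a different case: 1/3 against 1/2 DLTs in Cohort 1 moves the nearest dose from the second to the first. It does so only with posterior means, not medians, and the visible SAP text does not say which is used.
- *That early-withdrawal efficacy data drop out and Week 52 efficacy is completers only.* The model text is redacted and the SAP's version history describes a mixed model for repeated measures, so this cannot be established.

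**Conclusion.** The point holds as a gap in safety follow-up. After an irreversible infusion, the protocol permits removal for reasons other than consent and states no continued collection of new AEs to Week 52, while crude percentages keep the subject in the denominator. The likely direction is understatement of 52-week incidence. In the illustration the expected figure for a cohort of 3 falls from 25.0% to 18.8%, within a range of 16.7% to 25.0% depending on when events occur. These figures rest on an assumed event probability, one assumed removal at Week 12, and removal unrelated to the event. The documents report no withdrawals, so this is a loss that can happen, not one shown to have happened. The N-CRM consequence is secondary and gives no firm ground for saying a dose recommendation would change.

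**What to change.** In Protocol 7.1, with a matching sentence in 13.2.2, state that once DTX301 has been infused, ineligibility, deviation, noncompliance and AEs are recorded as such and the subject stays in safety follow-up to Week 52. The exceptions are withdrawal of consent, loss to follow-up, death and termination of the study. An administrative decision about a single dosed subject would then not end follow-up. Keep the full list of reasons for subjects not yet dosed.

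Optionally, show subject-weeks of follow-up beside AE incidence for each cohort in SAP 9.1. The duration data are already derived for SAP 5.4.

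The cost is one paragraph in the protocol and a few retained visits for subjects who would otherwise be removed. SAP 3.1 says enrollment in Cohort 4 has concluded, so the protocol wording helps only subjects still in follow-up. The subject-weeks display is useful regardless.
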